### 5.1. Ocular AEs

Ocular TE AEs include those with system organ class (SOC) = "Eye Disorders" or those with eye specified on the eCRF. The number and percentage of subjects who experienced at least 1 ocular TE AE will be presented in summary tables by preferred term according to MedDRA terminology as well as by affected eyes (events occurring in the treated eye only, in the fellow eye only, and in both eyes).

Serious ocular TE AEs will be summarized similarly.

Ocular TE AEs will be summarized by severity, and by relationship indicated on the eCRF (study treatment, device, and surgical procedure).

Ocular TE AEs will also be summarized by timing: for those with onset on or before the Week 4 visit date, and those with onset after the Week 4 visit date.

Individual subject ocular AEs will be presented in a data listing.

## 5.2. All AEs

The number and percentage of subjects who experienced at least 1 TE AE will be presented in summary tables by SOC and preferred term according to MedDRA terminology.

Serious TE AEs will be summarized and presented in a data listing.

Individual subject non-ocular AEs will be presented in a data listing.

### 5.3. Events of Special Interest

The events of special interest and how they are defined as per data captured in the clinical database are listed below.

• Retinal Detachment: A TE AE in the treated eye with preferred term "Retinal detachment" or a lowest level term (LLT) of "Rhegmatogenous retinal detachment",

"Central serous retinal detachment", "Haemorrhagic detachment of retinal pigment epithelium", "Detachment of macular retinal pigment epithelium", "Haemorrhagic detachment of retinal pigment epithelium" or "Vitreoretinal detachment".

- Significant choroidal hemorrhage: A TE AE in the treated eye with preferred term "Choroidal haemorrhage" or "Retinal haemorrhage" or LLT of "Choroidal bleeding", "Choroidal haemorrhage and rupture", "Expulsive choroidal haemorrhage", "Haemorrhagic choroidal detachment", "Retinal bleeding", "Bleeding intraretinal", "Retinal dot and blot haemorrhages", "Retinal blot haemorrhages", "Retinal haemorrhage spotted", "Subretinal haemorrhage", "Preretinal haemorrhage", or "Retinal nerve fiber layer hemorrhage". For these terms, the severity must be greater than mild (must be indicated as moderate or severe).
- Leakage of cells or need for vitrectomy: A "Yes" response to the Surgery and Delivery Device Details eCRF item "Was any IP visible in the vitreous after delivery?" on either surgery attempt (either the 1st or the 2nd attempt) or the text "vitrectomy" present in the Procedures eCRF item "Therapeutic or Diagnostic Procedures" with a start date/time on or after the date of surgery.
- Failure to deliver cells: A "No" response to the Surgery and Delivery Device Details eCRF item "Was the IP delivered to the target delivery location?" or a Surgical Deviation of "Dose of IP not fully administered". The response must be on the last surgery attempt for the subject (i.e., if there was a 2nd surgery attempt, the response must be on the 2nd attempt for that subject).
- Endophthalmitis: A TE AE in the treated eye with preferred term "Endophthalmitis" or LLT of "Acute endophthalmitis", "Chronic endophthalmitis", "Sterile endophthalmitis", "Aseptic endophthalmitis". "Infectious endophthalmitis", "Purulent endophthalmitis" or "Mycotic endophthalmitis".
- Significant loss of vision: defined as a decrease of ≥ 15 BCVA letters from baseline in the treated eye at the Week 4 visit. Unscheduled BCVA assessments after surgery prior to the Week 4 visit and assessments after Week 4 will not be considered here.

The Events of Special Interest will be summarized for the Safety Cohort. For each event, the count and percentage of subjects who had the event and the Exact Binomial 95% CI will be presented. Individual subject events will be presented in a data listing.

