A minimum of the first 3 eligible subjects at each center will receive active treatment in an uncontrolled, open-label Safety Run-in Phase to assess the safety of the surgical procedure and Delivery System, and to ensure the familiarity of the surgeons with the Delivery System and the procedure. The first 21 subjects from the designated Safety Cohort study sites will comprise the initial Safety Cohort. Enrollment into the safety Run-in Phase will be staggered across sites to ensure that the outcomes and learnings from earlier procedures can be transferred to all participating surgeons who will perform subsequent procedures. A 1-week interval for information sharing between the first few subjects is appropriate since most procedure-related AEs are expected to be apparent within hours of surgery.

Long-term Follow-Up Phase

After the 12-month acute phase of the study, subjects will be followed every 6 months for 2 years in the Long-term Follow-up Phase of the study, as shown in the Time and Events Schedule (see [Table 2](#)).

A DSMB will be established to monitor study data on an ongoing basis to ensure the continuing safety of the subjects enrolled in this study. Refer to Section [11.6](#), Data and Safety Monitoring Board, for details. The committee will meet periodically to review interim study data. After the review, the DSMB will make recommendations regarding the safety and continuation of the study. The details will be provided in a separate DSMB charter.

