4.2. Exclusion Criteria

Any potential subject who meets any of the following criteria will be excluded from participating in the study.

- 1.2 Subject has a history of neovascular (“wet”) AMD in the treatment eye, including any evidence of retinal pigment epithelium rips or evidence of subretinal or choroidal neovascularization or fluid. In cases where imaging is inconclusive, review of the case with the study site, considering history and imaging will determine eligibility. History or evidence of neovascular AMD in the fellow eye is allowed, if anti-vascular endothelial growth factor (VEGF) therapy has not been required for at least 8 weeks prior to screening.
2. Geographic atrophy secondary to any causes other than AMD in either eye
3. A diagnosis of glaucoma with an IOP ≥ 25 mmHg while being treated with an ocular hypotensive drug. Treatment should be no more than 1 drug preparation/combination, which can contain 1 or 2 ocular hypotensive active ingredients; subjects receiving more than 2 ocular hypotensive active ingredients are excluded. Note: subjects with a diagnosis of ocular hypertension (not glaucoma) are eligible to participate whether or not they are being medically treated.
4. Nuclear sclerotic cataract, cortical spoking, posterior subcapsular cataract above Grade 2 per Age-Related Eye Disease Study (AREDS) scale or any other ophthalmologic condition that reduces the clarity of the media that, in the opinion of the investigator or reading center, interferes with ophthalmologic examination (eg, corneal abnormalities, inadequate pupillary dilation), surgery or imaging in the study eye
5. Myopia >-8 diopters and subjects with >4 diopters of astigmatism, and $>+10$ diopters of hyperopia. Note: clinical evidence of retinal degeneration secondary to pathological myopia will exclude the subject as will a scleral ectasia with or without high myopia.
6. Evidence of other significant ophthalmologic disease (eg, glaucoma, intraocular inflammatory disease, diabetic retinopathy, Stage II, III, or IV macular hole, clinically evident vitreoretinal traction, choroidal or retinovascular disease, cystoid macular edema, significant epiretinal membrane, significant blepharitis, keratitis, conjunctivitis, or staphyloma) in the study eye

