11. STATISTICAL METHODS

Statistical analysis will be done by the sponsor or under the authority of the sponsor. A general description of the statistical methods to be used to analyze the efficacy and safety data is outlined below. In general, all data will be tabulated and displayed using descriptive methods only; no formal statistical testing is planned for outcome in the Safety Cohort.

Analyses will be conducted for all subjects who receive treatment in the open-label Safety Run-in phase.

After the first 21 subjects participating in the open-label safety run-in phase have completed 1 month of follow-up (the initial Safety Cohort), an analysis of data will be performed. These analyses will consist of simple descriptive statistics for key safety and efficacy measures, which will be described in the statistical analysis plan (SAP).

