### 1.4. Sample Size Justification

The sample size of 21 subjects is based on the number of subjects require to allow for an adequate clinical assessment of the safety and usability of the novel Delivery System.

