## 2.5. Analysis Sets

The initial Safety Cohort is defined as the first 21 subjects enrolled in the Open-label Safety Run-in Phase of the study who received surgery. Results will be presented as treatment group "CNTO 2476  $3.0 \times 10^5$  cells".

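### SAP 5.3 counts a vitrectomy in either eye towards the leakage/vitrectomy event of special interest, although the adverse-event and vision-loss events are limited to the treated eye

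*SAP*

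**What the plan says.** SAP 5.3 builds each event of special interest from database fields and reports, for the Safety Cohort, the number and percentage of subjects with an exact binomial 95% CI. SAP 2.5 defines that cohort as the "first 21 subjects enrolled in the Open-label Safety Run-in Phase of the study who received surgery".

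The leakage/vitrectomy event has two routes. The first is a Yes, at either surgery attempt, to the question whether product was visible in the vitreous after delivery. The second is a text match: the word vitrectomy "present in the Procedures eCRF item 'Therapeutic or Diagnostic Procedures' with a start date/time on or after the date of surgery". The second route gives a start date but no end date, and it does not mention the eye.

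The retinal detachment event combines a preferred term with a list of lowest level terms. Among these are "Detachment of macular retinal pigment epithelium" and the haemorrhagic form of pigment-epithelium detachment, which is listed twice.

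SAP 5.1 tabulates ocular treatment-emergent AEs by preferred term and affected eye, by severity, by recorded relationship to treatment, device and procedure, and by timing: "for those with onset on or before the Week 4 visit date, and those with onset after the Week 4 visit date". Serious ocular AEs are tabulated by preferred term and affected eye in the same way. SAP 5.3 applies neither the timing split nor the relationship split to its own rows.

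**The concern.** The event is meant to describe the operation and the device. Protocol 9.1.1.2 lists it for the safety review of the Delivery System, and Protocol 11.6 names it in the paragraph on device- or procedure-related events that could interrupt enrollment. The fellow eye is not operated on under the protocol, so a vitrectomy there says nothing about leakage from the delivery site.

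The fellow eye may nevertheless have disease of its own. Exclusion criterion 1.2 states: "History or evidence of neovascular AMD in the fellow eye is allowed". This does not make a fellow-eye vitrectomy likely, but it does mean the rule should not depend on none occurring.

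The study has a single arm and 21 subjects, and SAP 5.3 is the only place where the SAP asks for a confidence interval. A subject counted for the wrong eye would visibly change the rate, and there is no control rate against which to judge it.

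**Working it through.** **1. The six definitions side by side (SAP 5.3)**

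| Event | Eye named | Time limit |
|---|---|---|
| Retinal detachment (AE) | Treated | None after surgery |
| Significant choroidal hemorrhage (AE, moderate or severe) | Treated | None after surgery |
| Endophthalmitis (AE) | Treated | None after surgery |
| Leakage: product visible in vitreous | Operated eye, by nature | Surgery attempt |
| Need for vitrectomy | **None** | None after surgery |
| Failure to deliver cells | Operated eye, by nature | Last surgery attempt |
| Significant loss of vision | Treated | Week 4 visit only |

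The vitrectomy row is the only one in which the fellow eye can contribute.

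**2. Does another rule close the gap?**

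- SAP 2 says results are summarized by treated, fellow or both eyes where applicable. That governs how tables are laid out. It does not alter an event definition that names no eye.
- SAP 5.1 separates eyes, timing and relationship, but only for AEs. A vitrectomy identified from the Procedures page is not an AE record and does not enter those tables.
- The listing in SAP 5.3 would let a reader find the case by hand, but the tabulated rate and CI would still include it.

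**3. Size of one misplaced case**

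The plan has no calculated figure to reproduce. SAP 1.4 says "The sample size of 21 subjects is based on the number of subjects" needed for clinical assessment and gives no rate or precision. Protocol 11 adds that "no formal statistical testing is planned for outcome in the Safety Cohort". The check therefore uses the SAP's own statistic, the exact (Clopper-Pearson) 95% CI, with n = 21.

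- 0 events: the upper limit solves (1 − p)^21 = 0.025, so p = 1 − 0.025^(1/21) = 16.1%.
- 1 event: 1/21 = 4.8%. The upper limit solves (1 − p)^21 + 21p(1 − p)^20 = 0.025, giving 23.8%. The interval is 0.1% to 23.8%.
- 2 events: 2/21 = 9.5%, interval 1.2% to 30.4%.

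One wrongly counted subject adds 4.8 points to the rate and 23.8 − 16.1 = 7.7 points to the upper limit. The count moves only if that subject does not already qualify through visible leakage or a treated-eye vitrectomy.

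**4. What a timing split would show**

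SAP 5 counts AEs from surgery onward, ocular AEs are still collected after Month 12, and follow-up runs to Month 36. The documents give no background rate for any of these events. As an illustration only, assume a constant rate r of 1% to 10% per eye-year and 21 subjects followed throughout. The chance of at least one background case is 1 − exp(−21·r·t).

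| Assumed r | To Week 4 (t = 28/365.25) | To Month 36 (t = 3) |
|---|---|---|
| 1% | 1.6% | 46.7% |
| 2% | 3.2% | 71.6% |
| 5% | 7.7% | 95.7% |
| 10% | 14.9% | 99.8% |

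The table shows why an early row and a late row would be read differently. It does not estimate what will happen in this trial.

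**The case against.** The strongest reply is that SAP 5.1 already does most of the work. Retinal detachment, choroidal hemorrhage and endophthalmitis are all treated-eye ocular AEs. They therefore appear there by preferred term, relationship and Week 4 timing, and individual cases are listed. With 21 subjects and descriptive analysis, a late or unrelated event can be seen. This stands for those three events, although not for the combined rows of SAP 5.3. It does not reach vitrectomy, which is a procedure.

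It can also be said that the fellow-eye case is hypothetical, that the Procedures page may not be completed after Month 12, and that it may record the eye. The documents settle none of this. Neither schedule table has a row for procedures, so its absence from Table 2 proves nothing. If the eye is recorded, the fix is easier.

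Four stronger readings are tempting, and the documents do not support them.

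- *All these events run for 36 months, so AMD progression fills the rates.* Vision loss, failure to deliver and visible leakage are time-limited. For the others an open window is defensible. Protocol 1.2 describes a delayed route from leaked cells through membranes and traction to detachment, and Protocol 16.1 gives long-term safety of the cells as the reason for follow-up. The remark in Protocol 3.1 that "most procedure-related AEs are expected to be apparent within hours of surgery" supports a one-week pause between early subjects; it is not an analysis window.
- *The pigment-epithelium terms are AMD progression misfiled as retinal detachment.* The documents do not say so. Protocol 6.1 has a needle entering the subretinal space and raising a bleb, so such a detachment could be procedural.
- *These are the primary endpoint rates.* Protocol 9.2.2 makes safety endpoints primary as a class and names no event of special interest.
- *The earlier device's 5 of 33 serious retinal detachments (Protocol Table 3) can no longer be compared.* SAP 5.1 gives serious ocular AEs by preferred term and eye. Only the combined row in SAP 5.3 does not match.

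**Conclusion.** The point holds for vitrectomy. As written, SAP 5.3 lets a fellow-eye procedure count as a delivery event, its neighbouring definitions show that the treated eye was intended, and no other rule in the SAP prevents it. One case would move 0/21 (upper limit 16.1%) to 1/21 (upper limit 23.8%). This assumes that the text match is programmed literally and that the subject does not otherwise qualify. Whether such a case occurs, and how much background disease enters any of the rows, cannot be taken from the documents.

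The missing Week 4 split and the placement of the two pigment-epithelium terms are matters of presentation. Improving them is worthwhile because it is cheap, but the current text is not wrong on either. Overall this is a small drafting gap, and it gives no reason to doubt the safety analysis as a whole.

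**What to change.** **Correction.** In SAP 5.3, require the vitrectomy to be in the treated eye; a bilateral procedure would count. If the Procedures eCRF does not capture laterality, take it from the procedure record for each vitrectomy found.

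**Optional additions.**
- Keep the whole-study count and exact CI. Beside them, show retinal detachment, choroidal hemorrhage, endophthalmitis and vitrectomy by onset (for vitrectomy, procedure start date) on or before, and after, the Week 4 visit, each with its exact CI. A subject with both an early and a late event appears once in each row and once in the whole-study count.
- Show the two pigment-epithelium detachment terms as a separate line, so that detachment of the neurosensory retina can be read on its own, and delete the duplicate entry in the term list.

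**Cost.** One phrase of SAP text, a few more table rows for rare events, and possibly a manual check of any vitrectomy record. No new data collection is needed unless laterality is missing from the source. No event is hidden, because the whole-study counts and listings stay; a fellow-eye vitrectomy would leave only the event count.

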PGIC-Q								x	x	
CGIC								x	x	
Change in concomitant medications				<-----	Continuous----->					
Adverse events				<-----	Continuous----->					
Blood samples volume ⁱ		16.3 mL	0	0	20 mL ^k	16.3mL	10 mL	10 mL	10 mL	16.3 mL

BCVA=Best Corrected Visual Acuity; CGIC=Clinician Global Impression of Change; ETDRS=Early Treatment Diabetic Retinopathy Study; IOP=intraocular pressure; MN Read=Minnesota reading test; NEI-VFQ-25=National Eye Institute Visual Functioning Questionnaire; PGIC-Q=Patient Global Impression of Change – Quality of Life; PGIC-S=Patient Global Impression of Change – Symptoms; SD-OCT=spectral domain optical coherence tomography; SF-36=Short Form (36) Health Survey, FRI= Functional Reading Index questionnaire

Note 1: Screening procedures must occur within 45 days prior to treatment and may occur over multiple days. An additional optional pre-screening visit may be performed to determine potential subject BCVA for eligibility purposes. At the next screening visits, BCVA will be performed twice and the best value (lowest logMAR value) will be used as the subjects' baseline BCVA value.

Note 2: If a subject withdraws early from the Safety Run-in Phase, the end-of-study assessments (described in [Table 2](#)) should be performed.

- a) Subjects will be presented with an optional pre-screening ICF to allow the determination of their BCVA results prior to full study screening. The subjects who meet the BCVA eligibility criteria will be further screened to determine the full study eligibility. For the full study eligibility assessments, the subject will be presented a separate ICF within 45 days prior to treatment. The pre-screening visit is optional
- b) Best Corrected Visual Acuity testing includes BCVA using the ETDRS chart under high illumination and standardized conditions at 4 meters and 1 meter (as needed).
- c) Axial length should be recorded once at screening as a baseline measure. Any instrument may be used OR measurement taken from the subjects medical records may be utilized. Measurement, instrument and date of recording will be noted in the CRF.

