9.1.1.2. Open-label Safety Run-in Phase

The study will begin with a minimum of 7 surgeons performing approximately 3 open-label procedures to complete an initial Safety Cohort of 21 subjects. A minimum of 7 surgeons were chosen for the Safety Cohort based on the amount of users needed to identify complications with a surgical procedure and Delivery System. According to usability standards for medical devices, 5 to 8 surgeons performing 1 to 5 procedures at each site for a total of 21 procedures find between 75% and 90% of usability defects.¹⁶

After a total of 21 subjects are enrolled in the study, a safety review of the Delivery System and procedure will be performed. The data will be reviewed in a meeting with the surgeons, Principal Investigators, and the DSMB. The data will be assessed in the context of the predefined stopping rules described in the DSMB Charter. Events of special interest are choroidal hemorrhage, endophthalmitis or infections, retinal detachments, leakage of cells into the vitreous/need for vitrectomy, significant loss of vision defined as loss of ≥ 15 letters compared to baseline in the first month post-surgery, and failure to deliver cells/device failure.

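### SAP 5.3 reads early vision loss from the Week 4 BCVA alone and has no rule for a subject without one, so a qualifying loss at early withdrawal cannot be counted

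*SAP*

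**What the plan says.** Protocol 9.1.1.2 and 11.6 name six events of special interest. One is significant loss of vision, which 9.1.1.2 defines as a loss of at least 15 "letters compared to baseline in the first month post-surgery". Section 11.6 likewise limits it to the first month.

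SAP 5.3 makes the event narrower. It is "defined as a decrease of ≥ 15 BCVA letters from baseline in the treated eye at the Week 4 visit", and "Unscheduled BCVA assessments after surgery prior to the Week 4 visit and assessments after Week 4 will not be considered here". On the population, "The Events of Special Interest will be summarized for the Safety Cohort". As to the statistics reported, "the count and percentage of subjects who had the event and the Exact Binomial 95% CI will be presented". SAP 2.5 sets membership of that cohort by surgery, not by follow-up: it is "defined as the first 21 subjects enrolled in the Open-label Safety Run-in Phase of the study who received surgery".

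The protocol provides for early leavers. Note 2 to Table 1 begins "If a subject withdraws early from the Safety Run-in Phase, the end-of-study assessments" and says that these should be done; sections 9.1.1.3 and 10.2 ask for the same. The assessments are those of Table 2, which include BCVA.

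SAP 5.1 also depends on the Week 4 visit. One of its summaries splits ocular treatment-emergent AEs by timing: "for those with onset on or before the Week 4 visit date, and those with onset after the Week 4 visit date".

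**The concern.** Both SAP rules presuppose that the Week 4 visit took place, and neither says what to do when it did not. For vision loss the gap affects the result. An early leaver can have a post-operative BCVA that meets the protocol's definition, yet the SAP gives that value no route into the count. If the subject stays in the denominator, the unobserved outcome is treated as no event, which can lower the reported rate but never raise it. The row bears on the primary objective, the safety of the surgical approach and the Delivery System, and with 21 subjects a single event is visible in the percentage and the interval.

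For AE timing the stake is smaller. An event in a subject with no Week 4 visit date is neither on or before that date nor after it, so the two timing tables need not add up to the overall ocular AE table.

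**Working it through.** There is no figure in the plan to reproduce: this is an analysis rule, and the sample size of 21 has no statistical formula behind it.

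**Step 1. Follow one subject.** Take a subject who has surgery on Day 1 and withdraws at the Day 15 visit.
- Protocol Table 1 schedules no BCVA between surgery and Week 4.
- The only post-operative BCVA that the protocol asks for is therefore the one at early withdrawal (Table 1 Note 2; 9.1.1.3; 10.2; Table 2).
- If it shows a loss of at least 15 letters, the protocol definition is met, because Day 15 lies in the first month.
- Under SAP 5.3 the event cannot be recorded, because the value is not from the Week 4 visit. This is so whether or not the exit visit is labelled unscheduled.
- The subject had surgery and so belongs to the Safety Cohort.

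**Step 2. Look for a rule that fills the gap.**
- SAP 2.3 uses visits as recorded on the eCRF, without analysis windows, so the exit value is not mapped to Week 4.
- SAP 6.1 assigns 0 letters only when an assessment was done but could not be scored. It does not cover an assessment that never took place.
- SAP Attachment 1 completes event and medication dates, not visit dates.

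None of these helps.

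**Step 3. Size.** Inputs: N = 21 (SAP 2.5) and the exact binomial 95% CI (SAP 5.3), taken as Clopper-Pearson. For x events in n subjects the lower limit is the 2.5% point of Beta(x, n − x + 1), or 0 when x = 0, and the upper limit is the 97.5% point of Beta(x + 1, n − x). For x = 0 the upper limit is 1 − 0.025^(1/21) = 16.1%. The number of subjects without a Week 4 BCVA, m, is not in the documents. The table assumes m = 1 or 2.

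| Losses seen at Week 4 | m | Missing kept as no event | Missing excluded | All m had a loss, counted |
|---|---|---|---|---|
| 0 | 1 | 0/21 = 0% (0 to 16.1) | 0/20 = 0% (0 to 16.8) | 1/21 = 4.8% (0.1 to 23.8) |
| 0 | 2 | 0/21 = 0% (0 to 16.1) | 0/19 = 0% (0 to 17.6) | 2/21 = 9.5% (1.2 to 30.4) |
| 2 | 1 | 2/21 = 9.5% (1.2 to 30.4) | 2/20 = 10.0% (1.2 to 31.7) | 3/21 = 14.3% (3.0 to 36.3) |

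Changing only the denominator does little. The effect comes from an event that was measured but may not be counted, at 1/21 = 4.8 percentage points each. With m = 0 there is no effect.

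**Step 4. AE timing.** Under SAP 2.1 surgery is Day 1, so Week 4 is nominally Day 1 + 28 = Day 29. A study-day cut-off is therefore available for a subject with no Week 4 visit. It should not be imposed on everyone. Table 1 gives the Week 4 window as ±3 days (latest Day 32), whereas Protocol 9.1.1 allows ±3 business days. If Day 29 is a Wednesday, Thursday or Friday, three business days later is Day 34. A fixed Day 32 could thus fall before a compliant Week 4 visit and move events that SAP 5.1 places in the early table.

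**The case against.** The Week 4 rule looks deliberate and is defensible. Week 4 is the only scheduled BCVA in the first month, and SAP 3 repeats the restriction. Delivery itself creates a small retinal detachment (Protocol 12.1.1), so a common time point avoids counting transient post-operative loss. Barring later values agrees with the protocol's first-month limit. All of this stands for subjects who have a Week 4 BCVA. It does not settle what to do with those who have none.

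Three stronger readings are tempting, and the documents do not support them.
- A reader might infer that the SAP sets missing equal to no event. It never says so. That follows from the event definition and the cohort taken literally, but a programmer could equally use an evaluable denominator. The SAP leaves the choice open.
- A reader might infer that early leavers drop out of the early-safety tables. They do not. The other five events of special interest do not use the Week 4 visit. Ocular AEs also appear overall, for serious events, by severity, by relationship and in listings. An exit BCVA remains in the subject listing, and the by-visit BCVA table shows how many subjects were measured at Week 4.
- A reader might infer that the subjects lost are those with complications, so that the result is known to look too safe. That is plausible, but no section shows it, and Protocol 9.1.1.3 asks for every attempt to follow subjects to Month 36.

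It is also fair to say that the analyses are descriptive, that enrolment had ended by Amendment 3, and that nothing shows that any subject lacked a Week 4 visit.

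**Conclusion.** The point holds in a limited form. For a subject without a Week 4 BCVA, SAP 5.3 cannot count a loss that meets the protocol's first-month definition, and it does not state the denominator. Each such subject with a loss changes the row by 1/21, for example 0/21 against 1/21 with the intervals above. This rests on two assumptions that the documents do not settle: that at least one subject has no Week 4 BCVA, and that this subject lost at least 15 letters on a first-month measurement. The practical effect may be nil.

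The reach is one of six event rows and, through SAP 5.1, one supplementary AE split. A Week 4 visit held without BCVA affects only the vision-loss row, because the visit date still exists. It is worth correcting because the row serves the primary objective, the numbers are small and the change is cheap.

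**What to change.** **SAP 5.3.** Keep the Week 4 BCVA as the main value. Only where it is missing, use the early-withdrawal BCVA or the last unscheduled post-operative BCVA within the first month, and state the last study day of that period. Footnote each substituted value, since it may include transient post-operative loss. Report subjects with no post-operative BCVA in the period as not evaluable, with their number, and show the rate and exact interval over evaluable subjects and over all 21.

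**SAP 5.1 (minor).** Keep the Week 4 visit date as the cut-off where it exists. Use a nominal study day, for example Day 29, only for subjects with no Week 4 visit, so that their ocular AEs appear in a timing table. Give the number still in follow-up for the later table.

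**Protocol.** Reconcile the ±3 days in Table 1 with the ±3 business days in 9.1.1.

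The cost is a few sentences, a footnote and minor programming, with no new data collection. The drawback is that a substituted value may be earlier than Week 4; the footnote and its use only when Week 4 is absent limit this.
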